4 OBJECTIVES AND ENDPOINTS

Objectives and endpoints are no longer applicable per Protocol Amendment 01.

As of Protocol Amendment 01, only descriptive safety and investigator-assessed efficacy analyses will be conducted. No other analyses of efficacy, quality of life/patient-reported outcomes, PK, or health care resource utilization are planned. Previously collected biomarker samples may be analyzed, but no further collections are planned with Protocol Amendment 01.

Table 4-1: Objectives and Endpoints

Objectives	Endpoints
Primary	

• To compare the EFS per PRC of nivolumab plus BCG vs BCG alone in all randomized participants	
• EFS, defined as the time from randomization until any of the following events: recurrence (TaHG, T1 or CIS) or progression of disease, or death from any cause. For participants with CIS (+/- papillary disease) at study entry, a lack of complete response of the CIS component at the 13-week assessment will be considered an event.
Secondary	

• To compare the WFS of nivolumab plus BCG vs BCG alone in all randomized participants	
• WFS, defined as the time from randomization to progression to muscle invasive disease, cystectomy, systemic chemotherapy, radiotherapy, or death from any cause.

• To compare the OS of nivolumab plus BCG vs BCG alone in all randomized participants	
• OS, defined as the time from randomization to death from any cause.

• To evaluate the CRR at first disease assessment (Week 13) in all randomized participants with CIS (+/- papillary disease) at study entry by treatment arm (nivolumab plus BCG and BCG alone)	
• CRR, defined as the proportion of participants with CIS (+/- papillary disease) at study entry who are disease free at the first disease assessment.

• To evaluate the duration of response (DoR) in all randomized participants with CIS (+/- papillary disease) at study entry who achieved CRR at first disease assessment by treatment arm (nivolumab plus BCG and BCG alone)	
• DoR is restricted to participants with CIS (+/- papillary disease) at study entry who are disease free at the first disease assessment and is defined as the time between the date of the first CR to the date of first documented recurrence, progression, or death due to any cause.

• To describe the safety and tolerability of nivolumab plus BCG and BCG alone in all treated participants	
• Overall safety and tolerability will be measured by the incidence of AEs, SAEs, AEs leading to discontinuation, IMAEs, deaths, and laboratory abnormalities and changes from baseline.

Table 4-1: Objectives and Endpoints

Objectives	Endpoints
Tertiary/Exploratory	

 To evaluate the cystectomy-free survival (CFS) in all randomized participants by treatment arm (nivolumab plus BCG and BCG alone) 	
 CFS, defined as the time from randomization to cystectomy or death from any cause

 To evaluate the progression-free survival (PFS) per PRC in all randomized participants by treatment arm (nivolumab plus BCG and BCG alone) 	
 PFS, defined as the time from randomization to progression to muscle invasive or metastatic disease (T2+) of disease or death from any cause

 To evaluate disease specific survival (DSS) in all randomized participants by treatment arm (nivolumab plus BCG and BCG alone) 	
 DSS, defined as the time from randomization to death from UC

 To evaluate best overall CRR, as well as CRR at Week 26, at Week 52, and at Week 104 in all randomized participants with CIS (+/- papillary disease) at study entry by treatment arm (nivolumab plus BCG and BCG alone) 	
 Best overall CRR, defined as the proportion of participants with CIS (+/- papillary disease) at study entry who achieve disease free at any disease assessment during study treatment. CRR at different time points, defined as the proportion of participants with CIS (+/- papillary disease) at study entry who are disease free at each of the specified disease assessment time points (ie, Week 26, Week 52, and Week 104).

 To assess the participant's cancer-related symptoms and quality of life 	
 Change in subscales of the EORTC QLQ-C30 Change in subscales of the EORTC QLQ-NMIBC24

 To evaluate the participant's overall health status and utility for health 	
 Change in scores in both the EQ-5D-5L visual analog scale and the utility index

 To identify biomarkers that predict clinical efficacy 	
 Correlation of selected biomarkers with (EFS and PFS) and safety (incidence of AEs) endpoints

 To characterize nivolumab PK and immunogenicity in combination with BCG 	
 PK parameters, immunogenicity, exposure-response (E-R) relationships between select PK measures of exposure and safety and efficacy endpoints, if applicable

5 STUDY DESIGN

5.1 Overall Design

[figure not shown]
This is a Phase 3, randomized, double-blind, international, multicenter study of nivolumab in combination with BCG vs nivolumab-placebo with BCG in adult participants with high-risk NMIBC that is persistent or recurrent after treatment with BCG and does not qualify as BCG unresponsive.²¹

The study design schematic is presented in [Figure 5.1-1](#).

Figure 5.1-1: CA2097G8 Study Design Schematic

Stratification:

1. Histology: CIS (+/- papillary) vs T1
2. Time to recurrence from last BCG dose: Early vs Late
3. Intended BCG strain: TICE vs Other

The study will proceed through 3 phases: screening, treatment, and follow-up.

As of 02-Jun-2021, enrollment into this study was closed. Protocol Amendment 01 removes the decision points and the efficacy follow-up along with other study procedures. As a result, initial benefit/risk assessment by the Data Monitoring Committee (DMC) and PRC will be removed.

5.1.1 Screening Phase

As of 02-Jun-2021, enrollment into this study was closed. Therefore, the screening phase is no longer applicable per Protocol Amendment 01.

Not applicable per Protocol Amendment 01:

Screening begins by establishing the participant's initial eligibility and signing of the informed consent form (ICF). All screening tests must be completed as per the inclusion criteria ([Section 6.1](#)) and the time and events table ([Section 2 Table 2-1](#)). This includes complete excision of all papillary disease or CIS (if feasible) and biopsy of all suspicious lesions, urine cytology, and appropriate imaging of the chest, abdomen and pelvis. Screening tests that were performed as part of SOC do not need to be repeated.

Representative diagnostic pathology slides, obtained at TURBT within 90 days prior to randomization, which can be used to confirm the diagnosis of high-risk NMIBC and exclude the presence of tumor invasion into the muscularis propria, must be available. Tumor tissue samples (1-10 hematoxylin and eosin [H&E] stained slides), with at least one slide containing muscularis propria, preferably from the area of the bladder with the greatest disease burden, must be sent to independent Pathology Review Committee (PRC) for review. Confirmation of diagnosis by the PRC is required for randomization.

Sufficient, recent tumor tissue obtained within 90 days prior to randomization from the bladder tumor tissue obtained at TURBT (formalin-fixed paraffin-embedded block or 20 slides) will be submitted to the analytical laboratory for determination of PD-L1 expression and for biomarker studies. If less than 15 slides are available, please contact the Medical Monitor for discussion. Confirmation of receipt of acceptable tumor tissue by the analytical laboratory is required prior to randomization.

If sufficient tissue is not available within 90 days prior to randomization, then the site will be asked for additional tissue or a repeat TURBT will be required.

If tissue for diagnosis or biomarker assessment was obtained > 70 days prior to randomization, a repeat cystoscopy is required \leq 70 days prior to randomization to ensure there is no recurrent disease. See [Section 9.1.5](#) for further details.

Participants may not have received any systemic or intravesical anticancer therapy after the date that the submitted tumor tissue was obtained, with the exception of a single dose of intravesical chemotherapy at the time of TURBT. For participants with CIS, bladder mapping must be performed with random biopsy or with fluorescence cystoscopy with biopsy of all areas suspicious for disease.

Participants will be assessed for complete study eligibility prior to randomization as specified in [Table 2-1](#).

The screening phase ends with either confirmation of full eligibility and randomization of the participant or with the confirmation that the patient is a screen failure. This study permits reenrollment of a participant who discontinued the study as a pretreatment failure prior to randomization. If reenrolled, the participant must be reconsented. A new participant identification number will be assigned by the Interactive Response Technology (IRT) at the time of reenrollment.

5.1.2 Treatment Phase

The treatment phase begins with the randomization of the participant in the IRT system. The participant is randomly assigned to 1 of the 2 treatment arms as noted in the study schematic.

Stratification factors for randomization will include: disease status per PRC; time from last dose of BCG to recurrence per investigator; and intended BCG strain. Full details can be found in [Section 5.2](#).

During the treatment phase, participants will receive:

- **Arm A: Nivolumab 480 mg intravenous (IV) every 4 weeks (Q4W) for up to 24 months (104 weeks) and intravesical BCG (induction) weekly for 6 weeks followed by maintenance intravesical BCG weekly for 3 weeks at 3, 6, 12, 18, 24, 30, and 36 months (see [Table 7.1.2-1](#))**
- **Arm B: Nivolumab-placebo IV Q4W for up to 24 months (104 weeks) and intravesical BCG (induction) weekly for 6 weeks followed by maintenance intravesical BCG weekly for 3 weeks at 3, 6, 12, 18, 24, 30, and 36 months (see Table 7.1.2-1)**

For each arm, 1 treatment cycle equals 4 weeks. Day 1 of Cycle 1 will be the first dose of either study treatment.

The dose of BCG used for each weekly intravesical treatment will be based on current prescribing information for the particular BCG strain and preparation administered. This may vary as BCG strain and/or preparation administered may vary based on geographic region in which the participant is receiving treatment. Sites are required to declare which BCG strain they intend to use during the screening period for the purposes of stratification. BCG will be given at full dose, unless the dose is reduced due to lower urinary tract symptoms whilst on study (see [Section 7.4.2](#)).

For all participants, follow local standards of care for efficacy assessments.

5.1.3 Follow-up Phase

The follow-up phase will begin when the decision to discontinue a participant from the last study treatment is made (no further study treatment) or when 3 years of study treatment has been completed (eg, a participant may be discontinued from nivolumab/nivolumab-placebo study treatment on or before 24 months but remains on maintenance BCG study treatment for 36 months [see [Sections 5.4.4](#) and [5.4.5](#)]).

Participants must be followed for at least 100 days after last dose of last study treatment.

- Follow-up (FU) visit 1 should occur 30 days from the last dose (± 7) days or can be performed on the date of discontinuation if that date is greater than 42 days from the last dose.
- FU visit 2 occurs approximately 100 days (± 7 days) from last dose of study treatment.
- Both visits should be conducted in person.

Not applicable per Protocol Amendment 01:

Survival follow-up begins after FU visit 2.

- Survival follow-up visits occur every 3 months (± 14 days) until the end of the study.

Not applicable per Protocol Amendment 01:

Efficacy follow-up:

- Efficacy assessments occur until disease recurrence (other than low-grade Ta) or progression, per PRC (based on a positive urinary cytology, bladder biopsy, or imaging), or treatment discontinuation, whichever is later.
- For participants who have not had PRC confirmed progression or recurrence during the on-treatment period, efficacy assessments will continue as per [Table 2-3](#) and [Section 9.1.8](#).
- Where scheduling allows, efficacy follow up and survival follow up can coincide.

Treatment beyond disease recurrence/progression is not permitted except in the case of a low-grade papillary Ta tumor (TaLG) UC recurrence only, or for participants with CIS and/or Ta at Week 13 (see [Section 8.1.4](#)).

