BCG can be delayed, modified, or discontinued for BCG-related toxicity. Administration of BCG should not be delayed if nivolumab/nivolumab-placebo treatment is delayed.

The **follow-up phase** will begin when the decision to discontinue a participant from the last study treatment is made or when 3 years of study treatment has been completed. There will be a standard safety follow-up for a minimum of 100 days after last dose of last study treatment.

Not applicable per Protocol Amendment 01:

Survival follow-up begins after safety follow-up, with visits every 3 months until the end of the study. Efficacy assessments will occur until disease recurrence (other than low-grade Ta) or progression per PRC (based on a positive urinary cytology, bladder biopsy, or imaging) or treatment discontinuation, whichever is later.

Data Monitoring Committee: Yes; however, no longer applicable per Protocol Amendment 01

References:

- ¹ US Department of Health and Human Services, Food and Drug Administration, Center for Drug Evaluation and Research, Center for Biologics Evaluation and Research. BCG-unresponsive non-muscle invasive bladder cancer: Developing drugs and biologics for treatment guidance for industry. February 2018 (Accessed June 18, 2019).
- ² Steinberg RL, Thomas LJ1, Mott SL, O'Donnell MA. *Bacillus Calmette-Guérin (BCG) treatment failures with non-muscle invasive bladder cancer: A data-driven definition for BCG unresponsive disease.* Bladder Cancer 2016;2(2):215-24.

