Randomize	X	X	Participant will be randomized via IRT to Arm A or Arm B.
Dispense Study Drug	X	X	
First dose should be administered within 3 calendar days following randomization, but no earlier than ≥ 14 days following last TURBT/bladder biopsy.
 
Nivolumab/nivolumab-placebo will be administered at Day 1 of each cycle.
 
Bacillus Calumette-Guerin (BCG) will be administered as described in footnote “c.”

Safety Assessments			
Targeted Physical Examination, Measurements, Vital Signs, Performance Status	X		
For each cycle, weight, ECOG PS, blood pressure, heart rate, and temperature within 3 calendar days prior to dosing.
 
For Cycle 1 Day 1 and beyond, targeted physical examination to be performed only as clinically indicated.

Adverse Event (AE) Assessment (Including SAE)	Continuously		
Record at each visit. Collect continuously throughout the treatment period and for a minimum of 100 days following the last dose of study treatment.
 
All AEs (SAEs or non-serious AEs), including those associated with SARS-CoV-2 infection, must be collected continuously during the treatment period.
 
Participants will be followed for all SAEs and non-serious AEs of special interest (as defined in Section 9.2). All AEs (SAEs and non-serious AEs)

Table 2-2: On-treatment Procedural Outline for Arms A and B (CA2097G8)

Procedure ^a	Arm A: Nivolumab 480 mg IV Q4W Plus Intravesical BCG Arm B: Nivolumab-placebo IV Q4W Plus Intravesical BCG		
	Nivolumab/Nivolumab-placebo Visits^b Cycle 1 – Cycle 26 (Day 1 ± 3 days) (1 Cycle = 4 Weeks)	BCG Visits^{b,c} (± 3 days)	Notes ^d
			
associated with confirmed or suspected SARS-CoV-2 infection will be followed until:
 
 • Resolution • Condition stabilizes • Event is otherwise explained • Event is deemed irreversible • Participant is lost to follow-up (as defined in Section 8.3) • For suspected cases, until SARS-CoV-2 infection is ruled out 
See Section 9.2 for additional information on collection of AEs and SAEs.

Concomitant Medication Use	Continuously		Record at each visit.
Laboratory Tests			
CBC with Differential, Chemistry Panel Thyroid Testing	X		
Must be performed within 72 hours prior to nivolumab dosing. Refer to Section 9.4.4 for list of laboratory tests. Thyroid testing to be performed every 8 weeks (2 cycles).

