^c Participants in the study will receive one induction course of BCG (6 doses - 1 dose weekly for 6 weeks) followed by maintenance BCG for a total of 3 years treatment. Maintenance dosing includes 3 doses of BCG at weekly intervals at months 3, 6, 12, 18, 24, 30, and 36 (see [Table 7.1.2-1](#) for dosing detail by week). BCG dose will be administered \pm 3 days of nivolumab/nivolumab-placebo dosing (with a minimum of 5 days between BCG doses). BCG treatment should not be given within 14 days after TURBT/bladder biopsy. Fourteen days is the minimum requirement; BCG can be delayed greater than 14 days after TURBT/bladder biopsy based on routine clinical practice. BCG administration is independent of nivolumab/nivolumab-placebo cycles and study visits, however, where possible, BCG can be administered on the same visits as nivolumab/nivolumab-placebo, in which case assessments for both study treatments can be combined.

^d Some of the assessments referred to in this section may not be captured as data in the CRF. They are intended to be used as safety monitoring by the treating physician. Additional testing or assessments may be performed as clinically necessary or where required by institutional or local regulations.

Table 2-3: Follow-up Procedural Outline (CA2097G8)

Procedure	Follow-up ^a (FU) Visits 1 and 2	Not applicable per Protocol Amendment 01 Survival Follow-up ^b	Not applicable per Protocol Amendment 01 Efficacy Follow-up	Notes ^c
Safety Assessments				
Targeted Physical Examination, Measurements, Vital Signs, and Performance Status	See note			Weight, ECOG PS, blood pressure, heart rate, and temperature, to be performed only as clinically indicated.
Adverse Events Assessment (Including Serious Adverse Events)	X	See Notes	See Notes	
Record at each visit.
 
All SAEs and non-serious AEs should be collected continuously during the treatment period and for a minimum of 100 days following discontinuation of study treatment.
 
Participants will be followed for all SAEs, non-serious AEs of special interest (as defined in Section 9.2), and all AEs (SAEs and non-serious AEs) associated with confirmed or suspected SARS-CoV-2 infection until:
 
 • Resolution • Condition stabilizes • Event is otherwise explained • Event is deemed irreversible

Table 2-3: Follow-up Procedural Outline (CA2097G8)

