8.1.3 Post Study Treatment Study Follow-up

Per Protocol Amendment 01, efficacy follow-up is not required. Participants on efficacy follow-up at the time of Protocol Amendment 01 implementation at each site will conclude efficacy follow-up. Local standard of care assessments should be followed.

Participants will be followed for assessment of safety through 100 days post last dose of study treatment.

Not applicable per Protocol Amendment 01:

In this study, EFS is a key endpoint of the study. Post study follow-up is of critical importance and is essential to preserving participant safety and the integrity of the study. Participants who discontinue study treatment must continue to be followed (in this study or a rollover study) for collection of outcome and/or survival follow-up data as required and in line with [Section 5](#) until death or the conclusion of the study.

BMS may request that survival data be collected on all treated/randomized participants outside of the protocol-defined window ([Section 2, Table 2-3](#)). At the time of this request, each participant will be contacted to determine his/her survival status unless the participant has withdrawn consent for all contacts or is lost to follow-up.

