All nonserious AEs (not only those deemed to be treatment related) should be collected continuously during the treatment period and for a minimum of 100 days following discontinuation of study treatment.

Every AE must be assessed by the investigator with regard to whether it is considered immune-mediated. For events which are potentially immune-mediated, additional information will be collected on the participant's CRF.

9.2.3 *Follow-up of AEs and SAEs*

- Nonserious AEs should be followed to resolution or stabilization, or reported as SAEs if they become serious (see [Appendix 3](#)).
- Follow-up is also required for nonserious AEs that cause interruption or discontinuation of study treatment and for those present at the end of study treatment as appropriate.
- All identified nonserious AEs must be recorded and described on the nonserious AE page of the CRF (paper or electronic). Completion of supplemental CRFs may be requested for AEs and/or laboratory abnormalities that are reported/identified during the course of the study.

After the initial AE/SAE report, the investigator is required to proactively follow each participant at subsequent visits/contacts. All SAEs and nonserious AEs of special interest (as defined in [Section 9.2](#))

AEs (SAEs and non-serious AEs) associated with confirmed or suspected SARS-CoV-2 infection will be followed until resolution, until the condition stabilizes, until the event is otherwise explained, the event is deemed irreversible, or until the participant is lost to follow-up (as defined in [Section 8.3](#)), or for suspected cases, until SARS-CoV-2 infection is ruled out.

Further information on follow-up procedures is given in [Appendix 3](#).

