10.3.2 Safety Analyses

Limited safety analysis will be performed in all treated participants and will be described in the SAP.

Endpoint	Statistical Analysis Methods
Secondary	
Safety	Descriptive statistics of safety will be presented using NCI CTCAE version 5.0 by treatment group. All on-study AEs, treatment-related AEs, AEs leading to discontinuation, IMAEs, SAEs, and treatment-related SAEs, and deaths will be tabulated using worst grade per NCI CTCAE version 5.0 criteria by system organ class and preferred term. On-study laboratory parameters including hematology, chemistry, liver function, and renal function will be summarized using worst grade NCI CTCAE version 5.0 criteria. Events reported from the first dose up to and including 100 days following the last dose of study treatment could be included in estimating this incidence rate.

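### FU visit 2, now the last scheduled contact, may be held as early as day 93, so no scheduled contact covers new adverse events from then to the 100-day minimum

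*Combined protocol and SAP*

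**What the plan says.** **The visit.** Section 5.1.3 states that "FU visit 2 occurs approximately 100 days (± 7 days) from last dose of study treatment". Footnote a of Table 2-3 gives the same timing and window.

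**The minimum.** Section 5.1.3 also states: "Participants must be followed for at least 100 days after last dose of last study treatment". The Synopsis agrees: "There will be a standard safety follow-up for a minimum of 100 days after last dose of last study treatment". For AE collection, Table 2-2 requires it "for a minimum of 100 days following the last dose of study treatment", and Table 2-3 asks that events be "collected continuously during the treatment period and for a minimum of 100 days following discontinuation of study treatment". Section 9.2.2 sets the same minimum for nonserious AEs. Section 8.1.3, which carries Amendment 01 text, says: "Participants will be followed for assessment of safety through 100 days post last dose of study treatment".

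**What follows FU visit 2.** Nothing is scheduled. Section 5.1.3, Section 8.1.3 and Table 2-3 mark survival and efficacy follow-up as no longer applicable under Amendment 01. In Table 2-3 the AE row still refers to the notes in both of those columns.

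**The analysis.** Section 10.3.2 describes a limited, descriptive safety analysis. It allows counting of "Events reported from the first dose up to and including 100 days following the last dose of study treatment".

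**The concern.** The window is symmetric around 100 days, but 100 days is a floor. The early half of the window therefore lies below the period that the protocol requires.

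Before Amendment 01 this did little harm, because a later survival or efficacy contact could ask about the missing days in retrospect. With those contacts gone, a site that books FU visit 2 within the window can complete every scheduled contact before the required period has ended.

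At stake is the completeness of AE ascertainment in the last days of the safety period. Descriptive safety is one of only two kinds of analysis left after the amendment; the other is descriptive investigator-assessed efficacy. A new nonserious AE, or an SAE thought to be unrelated, that begins after an early visit could go unreported because nobody was scheduled to ask.

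**Working it through.** The plan gives no derived figure to reproduce here. The check is window arithmetic plus a reading of which contacts remain.

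**Inputs**
- FU visit 2: 100 ± 7 days from last dose (Section 5.1.3; Table 2-3, footnote a).
- Minimum follow-up and AE collection: 100 days (Synopsis; Tables 2-2 and 2-3; Sections 5.1.3 and 9.2.2).
- Former survival contacts: every 3 months ± 14 days from FU visit 2 (Section 5.1.3; Table 2-3, footnote b). I take 3 months as 13 weeks, or 91 days, as Section 9.1.3 does for cystoscopy.
- Enrollment: less than 5% of target (Synopsis; Section 3.1.1), with 700 participants planned for randomization (Section 5.2).

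**Step 1: largest gap.** The earliest visit is 100 − 7 = day 93 and the latest is 100 + 7 = day 107. After a day-93 visit, days 94 to 100 have no scheduled contact. That is 100 − 93 = 7 days, or 7/100 = 7% of the period.

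**Step 2: typical gap, assuming visits are uniform over the 15 permitted days.**
- Days before day 100: 93 to 99, so 7 of 15 visits (47%) are early.
- Total shortfall over those days: 7 + 6 + 5 + 4 + 3 + 2 + 1 = 28.
- Mean among early visits: 28/7 = 4 days.
- Mean over all visits: 28/15 = 1.9 days, just under 2% of 100 days.

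**Step 3: trial total.** 5% of 700 = 35 participants as an approximate ceiling. 35 × 28/15 = about 65 person-days, if all were treated and attended FU visit 2.

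**Step 4: what the amendment changed.** After a day-93 visit, the first survival contact would have fallen between 93 + 91 − 14 = day 170 and 93 + 91 + 14 = day 198. It came late, but could still have picked up events from days 94 to 100. That contact no longer exists.

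**Step 5: what remains after FU visit 2.** Known AEs are followed until they resolve or stabilize (Section 9.2.3). Unresolved drug-related laboratory toxicities are monitored locally (Section 9). Late SAEs believed to be related must be reported (Section 9.2.1). All three are triggered by something already known or by a suspected link to treatment. None prompts a question about a new event in a participant with nothing ongoing.

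**The case against.** The strongest reply is that a visit window and a collection period are separate obligations. AE collection is described as continuous, the 100 days is mandatory, and nothing says that FU visit 2 ends follow-up. A site that closed a participant out on day 93 would breach Section 5.1.3. This stands: both rules can be met, for example by a call on day 100. The schedule simply does not ask for one.

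Three stronger readings are tempting, and the documents do not support them.

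- *Sites are released after an early visit.* A reader might infer this from Section 9.2.1, which says investigators need not actively look for events in former participants. That sentence concerns people who have left the study. A participant on days 93 to 99 is still inside the mandatory period, and the same section requires all SAEs to be collected within 100 days of discontinuation of dosing.
- *The safety tables treat all 100 days as observed and count missed events as absent.* Section 10.3.2 is permissive: it says which reported events may enter the incidence estimate. It does not claim complete observation to day 100.
- *The end-of-study definition locks in the shortfall.* Section 5.3 ties completion to the procedures in Section 2, and Section 2 itself contains the 100-day AE minimum. Read in full, it supports the requirement.

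It is also fair to say that 7% applies only to a visit on exactly day 93, and that the window is the same in both arms.

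**Conclusion.** The point holds as a coverage gap of minor weight. The last scheduled contact may come up to 7 days before the minimum period ends, and after Amendment 01 no later scheduled contact makes up the difference. A reader might call the window and the minimum contradictory. They are not strictly so, because the duty to day 100 still binds sites.

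The loss is at most 7 days per participant seen early and averages about 1.9 days over all participants. It concerns fewer than about 35 people and a descriptive analysis with no hypothesis test.

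The size rests on three assumptions:
- Visits are uniform over days 93 to 107. The documents give no distribution of visit dates.
- The enrollment ceiling is 5% of 700. Participants already in screening on 02-Jun-2021 could still be randomized, so the final number may differ slightly.
- The 100 days run from last dose. Table 2-3 and Sections 9.2.1 and 9.2.2 count from discontinuation instead. If discontinuation is dated after the last dose, the gap grows by that interval, and these passages need to be reconciled.

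**What to change.** In Section 5.1.3 and in Table 2-3, footnote a, make the FU visit 2 window day 100 to day 107 (+7 days only). Alternatively, keep ±7 days and require a telephone AE check on or after day 100 whenever the visit is held early. Counted from last dose, either change cuts the uncovered time from at most 7 days to 0.

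In the same edit, use one starting point for the 100 days throughout, since neither change closes a gap that arises from counting from a later discontinuation date.

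The one-sided window needs a wording change in two places, adds no visit, and costs slightly less scheduling flexibility. The alternative keeps the flexibility but adds a short call for participants seen early.
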